Study Protocol

Official Title of the study: Effectiveness and safety of Chinese herbal medicine for hepatitis B virus-related acute-on-chronic liver failure: A multi-center, randomized and controlled trial

NCT number: not yet assigned

Date of the document: June 21, 2018

This prospective, multi-center, parallel, centrally randomized controlled trial was designed in accordance with the Consolidated Standards of Reporting Trials (CONSORT) and Standard Protocol Items: Recommendations for Interventional Trials (SPIRIT) guideline, which is led by the principal investigator from 302 military hospital in Beijing, will be carried out from September 2018 and December 2020 among 16 tertiary academic hospitals in China. Patients with hepatitis B virus (HBV) related Acute-on-chronic liver failure (ACLF) will be randomly allocated to the Chinese herbal medicine (CHM) group or the standard medical treatment (SMT) group in a 1:1 ratio. The last patient will be enrolled before August 2019 to make sure the availability of 48 week's survival status by the end of this study. We will decide whether to expand additional institutions to guarantee adequate enrolments after interim assessment of effective participant numbers around December 2018. Patients in the SMT group will receive the standard medical treatment, and patients in the CHM group will receive rhubarb decoction enema for 1 week and CHM for 8 weeks additionally. All patients will be followed at pre-designed time points after 8 weeks' observational period until August 30, 2020 for the primary outcome and secondary outcomes.

The study is consistent with Good Clinical Practice(GCP) guidelines and has been approved by 302 military hospital ethics review committee (2018007D). Written informed consent is requisite to be signed by the patients or the authorized person under the willingness. The privacy and data of all participants will be protected carefully before, during and after the trial.

Patients will be consented and enrolled by co-principal investigators at each institution and managed by care providers including residents, attending physicians and nurses according to the protocol. Most of the patients will be treated in hospital for 8 weeks so clinicians can supervise the administration of CHM, in addition, the policy of reimbursement filed by the lab results at determined time points will boost the regular follow-up of this study.

Diagnostic criteria

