The study will end at once if severe adverse events associated with CHM occurs or sufficient evidence indicates that adding CHM is not superior to the SMT group. Besides, CHM will discontinue and the final status will be censored in the condition of liver transplantation or the onset of liver cancer. Allocated interventions can be changed upon participant's request. All these changes will be recorded and analyzed based on intention-to-treat (ITT).

Intervention

Standard medical treatment

The SMT include a high-calorie diet; nucleoside analogues for HBV DNA-positive patients; sodium restriction, diuretics and paracentesis combined with albumin infusion for ascites; lactulose and L-ornithine aspartate and lactulose for HE and hyper-ammonia; hemostatic treatment for gastrointestinal hemorrhage; antibiotics for infections and renal replacement for HRS and uremic symptoms. CHM formulas, whatever routes of administration, are prohibited in the SMT group.

Chinese herbal medicine formula

There are two kinds of CHM based on traditional Chinese Medicines (TCM) syndromes. The common components of the two CHM formulas include *Artemisiacapillaris* Thunb (30g), *Salvia miltiorrhiza* Bge (30g), *Rhizoma*

Atractylodis Macrocephalae (30g), Rubia cordifolia L (30g), Sieyesbeckiaorientalis L (30g). Additional four components of Paeoniae Radix Rubra (60g), Gardenia jasminoides Ellis (9g), Hedyotis diffusa Willd (30g), Bletilla striata (15g) are involved for excess syndrome, and five other components of Astragalus membranaceus (30g), Radix Pseudostellariae (15g), Radix Aconiti Lateralis Praeparata (10g), Galli Gigeriae Endothelium Corneum (20g), Polygonum cuspidatum Sieb.et Zucc (15g) are involved for deficiency syndrome. All ingredients are manufactured as a Chinese herbal granule in a specific weight ratio to the raw herb (Beijing Kang Rentang Pharmaceutical Co., Ltd, Beijing, China) in accordance with the quality criteria of Chinese pharmacopoeia in 2015. Patients will take one dosage of CHM granule per day for 8 weeks. For patients who cannot take oral medicine can be switched to colon route by the colonic therapy system (IMS-100A produced by Sunny Medical in Beijing China).

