The randomized subjects who take at least one dose of CHM or SMT constitute the full analysis set (FAS) and those who complete all the visits constitute the per-protocol set (PPS). An efficacy assessment will be analyzed using FAS and PPS based on the principle of ITT. Subjects who have taken the CHM and been evaluated the safety at least once constitute the safety set (SS), which is used for safety evaluation. The statistical analysis will be performed using SAS 9.0 software (SAS Institute, Cary, NC, USA) by independent data management committee who are blind to the interventions.

Comparison of the two groups is conducted for the continuous variables with *t*-test and the categorical variables or rates with the chi-square test. The Kaplan-Meier overall survival curves will be generated and tested by log-rank. Cox proportional hazards regression model will be adopted to determine the prognostic factors associated with transplant-free survival. Multivariate logistic regression analyses will be adopted to explore factors associated with the incidence of liver-related complications. Subgroup analyses will be done based on the diagnostic criteria of Asian Pacific Association for the Study of the Liver (APASL) and European Association for the Study of the Liver (EASL) guideline.

The last observation carried forward approach was used for missing values. The statistical significance is defined as a two-sided $P < 0.05$.

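### The full analysis set requires a post-randomisation dose although the plan promises ITT; the wording has two readings, and only one of them could bias survival in favour of CHM

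*Combined protocol and SAP*

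**What the plan says.** Under Data management and Statistical methods, entry to the FAS depends on treatment intake: "The randomized subjects who take at least one dose of CHM or SMT constitute the full analysis set (FAS". The per-protocol set is limited to patients who complete every visit. The plan then states: "An efficacy assessment will be analyzed using FAS and PPS based on the principle of ITT". Neither set is all randomised patients, and no other efficacy set is defined.

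The section on discontinuing or modifying allocated interventions makes a similar promise. It says "Allocated interventions can be changed upon participant's request", and then "All these changes will be recorded and analyzed based on intention-to-treat (ITT".

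The design overview describes CHM as an add-on: "patients in the CHM group will receive rhubarb decoction enema for 1 week and CHM for 8 weeks additionally". The stopping criteria also speak of adding CHM. SMT is a package of supportive in-patient care, starting with diet and antivirals: "The SMT include a high-calorie diet; nucleoside analogues for HBV DNA-positive patients". No placebo or sham is described. The only parties said to be blind are the central laboratory and the data management committee that runs the analysis.

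**The concern.** Taking a first dose happens after randomisation. A population conditioned on it is not an ITT population, so the stated rule does not deliver the stated principle.

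Whether this matters in practice depends on what counts as a dose. SMT has no discrete first dose, and an in-patient in the SMT arm would qualify almost automatically. CHM is a separate product. The formula is chosen only after two senior physicians have judged the TCM syndrome, with a third if they disagree. A CHM patient could die, deteriorate or refuse before the first granule or enema. If that patient leaves the FAS while a comparable SMT patient stays, the arms are no longer comparable as randomised. If those who leave have a worse than average prognosis, transplant-free survival at week 12 is biased in favour of CHM.

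**Working it through.** **Inputs from the protocol.** SMT mortality 30.87% (Sample size; an 8-week rate, used here as a stand-in because no week-12 rate is given). Difference 12 points, which gives 18.87% under CHM if read as the expected effect. 255 per group, 10% attrition, power 0.80, two-sided 0.05.

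**Inputs assumed.** The number of undosed CHM patients and their mortality. The documents give neither, so ranges are shown.

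**The plan's own figure.** A margin-type formula with both arms at the control rate comes close: 2 × 0.3087 × 0.6913 × (1.960 + 0.842)² / 0.12² gives 233, and 233/0.9 gives 259 (or 233 × 1.1 gives 257), against the stated 255. The usual comparison of 30.87% with 18.87% gives 203, or 226 after attrition. This point does not depend on which was used.

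**Reading 1: a dose of either CHM or SMT counts in either arm.** CHM patients also receive SMT, so an in-patient who never takes CHM still meets the condition. The FAS is then close to all randomised, and the bias is close to zero.

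**Reading 2: a dose of the allocated treatment is required, and only CHM patients fail it.** Assume no true effect. Expected deaths per arm are 0.3087 × 255 = 78.72. If k CHM patients are dropped and a fraction m of them die, the remaining CHM mortality is (78.72 − k·m)/(255 − k).

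| k dropped | m | CHM mortality in FAS | Spurious benefit (points) |
|---|---|---|---|
| 5 | 0.3087 | 77.18/250 = 30.87% | 0 |
| 5 | 0.50 | 76.22/250 = 30.49% | 0.4 |
| 5 | 1.00 | 73.72/250 = 29.49% | 1.4 |
| 10 | 0.3087 | 75.63/245 = 30.87% | 0 |
| 10 | 0.50 | 73.72/245 = 30.09% | 0.8 |
| 10 | 1.00 | 68.72/245 = 28.05% | 2.8 |

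**Effect on the error rate under reading 2.** With d the spurious difference, the chance of a significant result favouring CHM is 1 − Φ((1.96·se₀ − d)/se₁). Here se₀ is the pooled and se₁ the unpooled standard error, with 255 patients in one arm and 255(1 − f) in the other, and f the share of the CHM arm dropped. The nominal value is 2.5%.
- f = 2% (about 5 patients): 2.5% at average mortality, 3.1% if half die, 5.3% if all die.
- f = 5% (about 13 patients): 2.5%, 4.3% and 14.3%.

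**Cost of analysing all randomised patients.** Suppose undosed CHM patients have SMT mortality and dosed patients 18.87%. With 2% undosed, the CHM rate is 0.98 × 0.1887 + 0.02 × 0.3087 = 0.1911. Power is Φ((d√n − 1.96√(2p̄(1 − p̄))) / √(p₁(1 − p₁) + p₂(1 − p₂))), where d = p₁ − p₂ and p̄ is the mean of the two rates.
- 255 per arm: 0.882 with none undosed, 0.868 with 2%, 0.845 with 5%.
- 229 per arm (255 × 0.9): 0.846, 0.830 and 0.805.

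**The case against.** The strongest reply is that the literal text already keeps undosed CHM patients. It asks for CHM or SMT, and the CHM arm receives SMT as well. The same section defines the safety set by intake of CHM alone, so the authors named CHM as the condition where they wanted it and did not do so for the FAS. This is a fair argument for reading 1. It does not settle the matter, because CHM and SMT are also the names of the two groups, so the phrase can equally mean each group's own treatment.

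Some routes to exclusion are also partly covered. The rule on changed interventions promises ITT for a patient who asks to switch. A colonic route is provided for those who cannot take oral medicine. The listed contraindications concern the enema only. Several severe complications are excluded at entry, so deaths before a first dose may be few. All of this stands and makes a large number of exclusions less likely. It does not remove refusal or death before the first dose. The promise of ITT for switches also conflicts with the FAS rule if the allocated treatment is what must be taken.

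A reader might infer that exclusions will fall mainly on the CHM arm, or that everyone knows the allocation. The documents support neither as stated. The first holds only under reading 2. As to the second, the laboratory and the data management committee are said to be blind. What can be said is that patients and clinicians appear to know the allocation, since no placebo is described; the trial is never called open-label.

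**Conclusion.** The point holds as a conflict between the stated principle and the defined population. FAS entry depends on a post-randomisation event, ITT is promised in two places, and no all-randomised set exists.

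A one-sided bias is possible but not established. It requires reading 2, some CHM patients who never start, and worse than average mortality among them. With 5 to 10 such patients the spurious benefit runs from 0 to 2.8 points, against the planned 12. The upper end assumes that every dropped patient dies, and 1.4 or 2.8 points should not be quoted as the expected size. The range uses an 8-week mortality rate for a week-12 outcome and assumes no true effect.

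**What to change.** Replace the FAS definition with one sentence: for the primary and secondary efficacy analyses, the FAS is all randomised patients, analysed in the arm allocated, whether or not any dose was taken. Keep dose conditions for the safety set only.

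The change needs no extra patients or visits. Under reading 1 it alters almost nothing. Under reading 2 it removes the selection. The downside is the slight dilution shown above if some CHM patients never start: at 255 per arm, power goes from 0.88 to about 0.87 with 2% undosed.

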In addition, patients in the CHM group will also receive daily herbal enema of 100 microliter decoction composed by Radix et Rhizoma Rhei Palmati (Dahuang) 30g and Fructus Mume (Wumei) 30g for 7 days expect the following contraindications: (1) severe hemorrhoid, (2) female patients during menstruation, (3) anal stenosis, (4) artificial anal and (5) cardiac disease.

Outcome measurements

Primary outcome

The primary outcome is transplant-free survival at week 12.

Secondary outcomes

Secondary outcomes include (1) transplant-free survival at week 24, (2) the influence on liver function assessed by MELD score (involving levels of serum bilirubin, creatinine, INR and sodium) at week 12, (3) the influence on liver function assessed by Child-Pugh score (involving the serum bilirubin, coagulation function, albumin and the complication of hepatic encephalopathy and ascites) at week 12. (4) quality of life assessed by WHOQOL-BRIEF at week 12 and (5) the incidence of serious complications (including infections, encephalopathy, HRS, and gastrointestinal bleeding) from week 1 to week 24.

Safety outcomes

Primary vital signs, physical examinations, electrocardiogram and some laboratory tests such as routine blood test, urine test, renal function will be assessed before and after treatment to monitor the safety of this study. Furthermore, adverse events are also recorded in a predesigned case report form (CRF) through the whole study period. An independent safety committee will analyze the incidence and severity of adverse events to identify any unexpected adverse events or mortality in the CHM groups.

Other assessed parameters

Epidemiological characteristics, the details of nucleoside/nucleotide analog therapy, family history of liver disease were collected from patient medical record, the level of HBV DNA, endotoxin, and lymphocyte subsets were tested as well as CLIP-C-ACLF score were computed at week 24 and 48. The plasma level of HBV DNA, endotoxin, and cytokines were tested in ADICO clinical laboratories (Shanghai, China) which is blind to the allocation information. Remnant plasma will be stored at -80°C for ancillary studies. Women of childbearing age will undergo pregnancy test for the eligibility.

Sample size

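### The per-protocol set requires every visit to be completed with no exception for death, so read literally it holds no deaths by week 12

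*Combined protocol and SAP*

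**What the plan says.** All references are to the combined protocol and SAP.

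- **Data management and Statistical methods.** The full analysis set (FAS) is randomised patients with at least one dose. The PPS has a single criterion: "those who complete all the visits constitute the per-protocol set (PPS". Both sets are used for efficacy: "An efficacy assessment will be analyzed using FAS and PPS based on the principle of ITT". For survival, "The Kaplan-Meier overall survival curves will be generated and tested by log-rank"; rates are compared by chi-square. Missing values are carried forward.
- **Outcome measurements.** "The primary outcome is transplant-free survival at week 12". The first secondary outcome is "transplant-free survival at week 24".
- **Other assessed parameters.** "CLIP-C-ACLF score were computed at week 24 and 48".
- **Opening overview.** Follow-up is at pre-specified times that are not listed, until August 30, 2020. Recruitment is timed so that survival at 48 weeks is known: "The last patient will be enrolled before August 2019 to make sure the availability of 48 week".
- **Criteria for discontinuing or modifying allocated interventions.** Final status is censored at liver transplantation or onset of liver cancer. "Allocated interventions can be changed upon" the participant's request, and such changes are recorded and analysed by intention to treat.
- **Standard medical treatment.** CHM by any route is forbidden in the standard medical treatment (SMT) group.

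No section says how death bears on completing the visits. None adds a PPS criterion for treatment received, adherence, eligibility or deviation.

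**The concern.** A per-protocol analysis is normally run to see whether the main result holds among patients treated and followed as planned. That works only if membership does not depend on the outcome. Here the outcome is largely death, and a dead patient cannot attend the remaining visits. The rule therefore selects on the endpoint and takes out the deaths that the two arms are meant to be compared on. If CHM lowers mortality, it also removes more SMT than CHM patients, so those who remain are no longer the groups that were randomised.

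What is at stake is the PPS efficacy result. Reported as the text stands, it could not confirm or question the FAS on week-12 deaths, although the plan names it for efficacy. If the rule is left ambiguous, whether roughly a quarter of the patients belong to the set may be decided after outcomes are known.

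**Working it through.** **1. Which deaths the rule removes.** The visit schedule is not given, so the answer depends on what counts as all the visits.

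| Reading | Effect on deaths |
|---|---|
| Visits of the 8-week treatment period only | Earlier deaths removed; deaths from week 8 to week 12 stay |
| Visits to week 24 or week 48 | All deaths by week 12 removed, and all deaths by week 24; deaths after the last visit stay |
| Visits due while alive | No death removed |

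The plan sets assessments at weeks 24 and 48, so the second row is the literal reading. Carrying the last observation forward does not change this. It fills missing values and does not decide who is in the set.

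**2. Size.** The plan gives no PPS size to reproduce and no week-12 mortality. The illustration uses the 8-week planning figures; cumulative deaths by week 12 cannot be fewer.

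Inputs, from Sample size unless marked:
- 255 per group, taken as given (its derivation does not bear on a set definition)
- SMT 8-week mortality 30.87%
- CHM 8-week mortality 18.87%: an assumption, reading the stated -12% as an absolute difference (30.87 - 12)

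Expected exclusions = n × mortality:
- SMT: 255 × 0.3087 = 78.7, about 79 (31%)
- CHM: 255 × 0.1887 = 48.1, about 48 (19%)
- Total: 126.8 of 510 = 24.9%
- Remaining at most: 176.3 + 206.9 = 383.2, about 383 of 510 (75%), with 0 deaths in either arm by week 8; on the second row of the table, 0 by week 12

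If 10% are first lost independently of outcome, 229.5 per group remain. About 71 SMT and 43 CHM deaths are then removed, leaving about 159 and 186.

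Range over the unknown CHM rate:

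| CHM 8-week mortality | CHM deaths removed | Total removed of 510 |
|---|---|---|
| 18.87% (12 points lower) | 48.1 | 126.8 (24.9%) |
| 27.17% (12% lower in relative terms, 0.3087 × 0.88) | 69.3 | 148.0 (29.0%) |
| 30.87% (no effect) | 78.7 | 157.4 (30.9%) |

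The share removed is 25% to 31% throughout. The imbalance between arms is the treatment effect itself: 12 points in the first row, none in the last.

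**3. Transplantation.** A transplanted patient can attend every visit and stay in the PPS. If transplant counts as an event, as the endpoint's name implies, the PPS keeps transplant events and loses deaths. If final status is censored at transplant, as the discontinuation section says, the PPS has no events by week 12. The two passages must be reconciled before the PPS result has a defined meaning.

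**4. Treatment received.** An SMT patient who takes CHM, which the plan forbids, and attends every visit satisfies the only PPS criterion. This holds however death is handled. The documents give no basis for estimating how often it would happen.

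**The case against.** The strongest reply is that in a survival trial, completing the visits naturally means the visits due while the patient lives, so this is loose wording and not a plan to analyse a set without deaths. That may well be the intention. But the clause is the only rule given, nothing in the document qualifies it, and someone applying it as written would drop the deaths.

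A second reply is that the FAS leads. The intention-to-treat wording does imply this, and the FAS is untouched by the PPS definition. The same sentence, however, applies that label to both sets and does not call the PPS supportive.

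Three stronger readings are tempting and not supported:

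- **That every patient who dies is excluded.** Only deaths before the last scheduled visit are. Follow-up runs to August 30, 2020, so a patient enrolled in late 2018 could die after a week-48 visit and stay in. The log-rank test on overall survival could then still have late events.
- **That no PPS test of the primary outcome is possible.** This is true for deaths by week 12. For transplant-free survival it is true only if transplant is censored.
- **That all patients who change treatment must leave the PPS.** The plan permits changes on request and assigns them to intention to treat. Whether a permitted switch disqualifies a patient is a design choice. Prohibited CHM use in the SMT group is the clear deviation.

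**Conclusion.** The point holds for the PPS as written. Completion of all visits is the sole criterion, death is not exempted, and assessments extend to weeks 24 and 48, so membership depends on the primary outcome and no deaths by week 12 remain in either arm. At the planning rates about 79 SMT and 48 CHM patients, 25% of 510, would be excluded. This rests on the literal reading, on 8-week rates standing in for week 12, and on an assumed CHM rate of 18.87%. The defect itself depends on none of these figures.

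A reader might infer that the trial's main result is biased. The documents do not support that, because the FAS keeps these patients. The missing treatment criterion is a real but secondary weakness. This should be fixed, and the fix is simple.

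**What to change.** **Main change.** Add to the PPS definition that a patient who completed all visits due before death or transplant meets the visit criterion, so that neither event is ever counted as an incomplete visit. Reconcile this with the censoring at transplantation in the discontinuation section, so that one rule governs transplant in the transplant-free survival endpoint.

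**Secondary changes.** Exclude from the PPS the SMT patients who took prohibited CHM. Have the sponsor decide, before data are seen, how permitted switches on request are handled. State that the PPS is supportive to the FAS.

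**Cost.** The main change is one sentence. It is best made before enrolment begins in September 2018, and at the latest before database lock. The secondary change requires prohibited CHM use to be recorded in the case report form; the plan records changes of intervention but specifies no such record. A PPS conditioned on treatment received also stays open to post-randomisation selection, since patients who deteriorate may be the ones who change treatment. That is a further reason to read it only as support.

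### The safety set contains only patients who took CHM, so general adverse events and safety tests have no planned comparison with SMT

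*Combined protocol and SAP*

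**What the plan says.** Data management and Statistical methods defines three analysis sets in one paragraph.

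- Full analysis set: "The randomized subjects who take at least one dose of CHM or SMT constitute the full analysis set (FAS". Both treatments are named.
- Use of the full analysis and per-protocol sets: "An efficacy assessment will be analyzed using FAS and PPS based on the principle of ITT". Neither is assigned to safety.
- Safety set: "Subjects who have taken the CHM and been evaluated the safety at least once constitute the safety set (SS), which is used for safety evaluation". Only CHM is named.

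Under Safety outcomes, the plan lists vital signs and physical examination, and adds: "electrocardiogram and some laboratory tests such as routine blood test, urine test, renal function will be assessed before and after treatment". It also states that "adverse events are also recorded in a predesigned case report form (CRF) through the whole study period". Neither statement is limited to one arm. The independent safety committee, however, is to analyse adverse events "to identify any unexpected adverse events or mortality in the CHM groups", with no mention of SMT.

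Two further provisions decide who can enter the safety set. The section Standard medical treatment bars CHM formulas in the SMT group. The section on discontinuing or modifying interventions says "Allocated interventions can be changed upon" a participant's request.

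**The concern.** CHM is given on top of SMT, in patients for whom the Sample size section takes an 8-week mortality of 30.87% on SMT. Many adverse events and abnormal tests will therefore occur whatever the allocation. An incidence among CHM patients alone mixes this background with any harm from CHM, and only a concurrent SMT group can separate the two.

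The trial's title promises evidence on safety as well as effectiveness. If the plan is followed as written, half of that claim rests on a single-group table for every harm that is not already an efficacy outcome. A comparison added after the results are known would be post hoc. The plan also ends the study if severe adverse events associated with CHM occur, and association is harder to judge without a control rate.

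**Working it through.** **1. Who is in the safety set.** Entry requires having taken CHM. CHM is prohibited in the SMT group, so a patient treated with SMT alone cannot enter. An SMT patient who switches on request does enter, but as an exposed patient and not as a comparator. The set therefore contains no SMT-only patients by definition.

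**2. What keeps a comparison.** Transplant-free survival, MELD and Child-Pugh are efficacy outcomes analysed in both arms. So is secondary outcome 5, "the incidence of serious complications (including infections, encephalopathy, HRS, and gastrointestinal bleeding) from week 1 to week 24". What loses its comparator is all other adverse events, vital signs, physical examination, ECG, and the blood and urine tests that are not part of MELD or Child-Pugh.

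**3. How many patients are left out.** The Sample size section gives 255 per group, so the total is 2 × 255 = 510.

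- No switching: 255/510 = 50%.
- 5% of SMT patients switch (assumed): 255 × 0.95 ≈ 242.
- 10% switch (assumed): 255 × 0.90 ≈ 230.

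**4. What a two-arm analysis would deliver.** The plan gives no adverse-event rate and no power statement for safety, so there is no figure to reproduce. I assume background rates p of 5% to 30%.

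- Precision: 95% CI half-width for a risk difference at equal rates = 1.96 × √[2p(1−p)/n]. For p = 20% and n = 255: 1.96 × √(0.32/255) = 6.9 points.
- Detectable excess d over SMT rate p₀ (two-sided 0.05, power 0.80): solve n = [1.96√(2p̄(1−p̄)) + 0.842√(p₀(1−p₀)+p₁(1−p₁))]²/d², with p₁ = p₀ + d and p̄ the mean of p₀ and p₁.

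| Assumed SMT rate | Half-width, n = 255 | Detectable excess, n = 255 | Half-width, n = 230 | Detectable excess, n = 230 |
|---|---|---|---|---|
| 5% | ±3.8 | 6.9 | ±4.0 | 7.3 |
| 10% | ±5.2 | 8.7 | ±5.5 | 9.2 |
| 20% | ±6.9 | 10.8 | ±7.3 | 11.4 |
| 30% | ±8.0 | 11.9 | ±8.4 | 12.5 |

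All table entries other than the rates are percentage points. The 230-per-arm columns apply the plan's 10% attrition (255 × 0.90).

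**5. What the CHM-only table hides.** Suppose 20% of 255 CHM patients have a given event. The plan as written reports 20% ± 1.96 × √(0.2 × 0.8/255) = 20% ± 4.9 points, whatever happens on SMT.

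- If the SMT rate is 10%: the excess is 10.0 points, half-width 1.96 × √[(0.16 + 0.09)/255] = 6.1, 95% CI 3.9 to 16.1.
- If the SMT rate is 20%: the excess is 0, 95% CI −6.9 to 6.9.

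The first case is clear evidence of harm and the second is none. The planned table looks the same in both.

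**The case against.** **It may be a drafting slip.** The full analysis set names both treatments a few lines earlier, so the safety definition may simply have lost SMT. The methods text also announces two-group comparisons of continuous and categorical variables without confining them to efficacy. This is a fair reading of intent. But that general sentence does not mention safety data, and the set assigned to safety has no second group to test. The safety committee's remit repeats the restriction to CHM, which makes a slip less likely. A slip would still need correcting, because an analyst following the text would produce a CHM-only table.

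**The data exist.** Adverse-event recording has no stated arm limit, so an excess could be estimated later. That stands: the gap is in the planned analysis and not, so far as the text shows, in data collection.

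**Switchers have a stated rule.** The plan says changes of intervention are recorded and analysed by intention to treat. That does not alter who has taken CHM, and the statistical section attaches that principle to efficacy. The two passages should nevertheless be reconciled.

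**The 230-per-arm columns are pessimistic.** One safety evaluation is enough for entry, so later dropouts stay in the set. This is right, and those columns are only a sensitivity range. Under grouping by treatment received, 10% switching would give about 280 against 230 (255 + 25.5 and 255 − 25.5), with a detectable excess of 7.0 to 12.0 points, close to the 255-per-arm result.

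**Grouping by treatment received is not a randomised comparison once patients switch.** Also right, which is why a table by randomised arm belongs beside it.

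**Conclusion.** The point holds. As written, the safety evaluation covers only patients who took CHM, and the plan contains no comparison with SMT for adverse events and safety tests outside the efficacy outcomes. Up to 255 of 510 planned patients (50%) are left out. A two-arm analysis of 255 per group would estimate risk differences to within ±3.8 to ±8.0 points and detect an excess of 6.9 to 11.9 points with 80% power. The plan provides for neither.

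The 50% follows from the plan's own sample size, with no switching. The precision and power figures rest on assumed event rates of 5% to 30%, and the smaller counts outside the set on assumed switching of 5% or 10%. The primary outcome and the major clinical harms listed as efficacy outcomes are not affected. This should be fixed before database lock; it does not threaten the main efficacy result.

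**What to change.** 1. Define the safety set as all randomised patients who received any study treatment, whether CHM plus SMT or SMT alone, grouped by treatment received. State whether the existing condition of at least one safety evaluation is kept, and apply it identically to both groups.
2. State how patients who switch are classed, and add a sensitivity table by randomised arm.
3. Report adverse-event incidence in both groups with risk differences and 95% CIs. Report changes in vital signs, ECG and laboratory safety tests for both groups.
4. Reword the safety committee's remit under Safety outcomes so that it reviews both arms.

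The cost is SAP wording and additional table columns before database lock. The plan states no arm limit on adverse-event recording in the CRF, so no new data collection appears to be needed. The sponsor should confirm that SMT patients' adverse events and safety tests are in fact being recorded.
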